6.2.2. Reactogenicity Data

Reactogenicity data is solicited adverse events (AEs). The reactogenicity data collected from e-Diary will be: local reactions (redness, swelling, and tenderness at injection site), systemic events (loss of or decreased appetite, drowsiness [increased sleep], and irritability [fussiness]), temperature and use of antipyretic medication.

The e-Diary will record reactogenicity data from day 1 to day 7 for each vaccination. The analysis interval for reactogenicity data after each vaccination will be ‘any day 1-7’ which includes data from day 1 to day 7. The day of vaccination is considered as day 1.

Table 3. Analysis Interval for Reactogenicity Data

#	Analysis Interval	Analysis Population	Interval Start date (inclusive)	Interval Stop (inclusive)
1	vaccination 1	Vax 1 Safety	Vax 1 date	Vax 1 date + 6 days (or until resolved day)
2	vaccination 2	Vax 2 Safety	Vax 2 date	Vax 2 date + 6 days (or until resolved day)
3	vaccination 3	Vax 3 Safety	Vax 3 date	Vax 3 date + 6 days (or until resolved day)
4	any vaccination	Safety	Vax 1, Vax 2, or Vax 3	Vax 1, Vax 2, or Vax 3+ 6 days (or until resolved day)

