For subjects experiencing any local reactions (or those with derived reaction presence in Table 4), the maximum duration (last day of reaction –first day of reaction +1) will be derived for each vaccination. Resolution of the event is the last day in which the event is recorded in the e-Diary or the date the event ends if it is unresolved during the subject diary-recording period, unless chronicity is established.

In summary, the following variables will be derived for local reaction:

1. Each local reaction on each day (up to day 7) after each vaccination.
2. Each local reaction on ‘any day 1-7’ after each vaccination and any vaccination.
3. Maximum severity of each local reaction on ‘any day 1-7’ after each vaccination and any vaccination.
4. Maximum duration of each local reaction after each vaccination.
5. Any local reaction on ‘any day 1-7’ after each vaccination and after any vaccination.

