10.1.4.2.2. Calculation of Duration with Nonmissing Symptom Resolved Date

The symptom resolved date page can be filled in a scheduled visit which can have the symptom resolved page filled at unscheduled visit. In the programming handling, all of the CRF pages will be pooled together regardless the page origin. If the symptom resolved page indicated the symptom is continuing, the duration will be counted as ‘Unknown’.

First, the program logic will find all of the e-Diary events with the symptom present on the last day of the e-diary entry. It may not necessarily be day 7. For example, if subject’s e-diary is only transmitted until day 6, as long as the event is present on day 6, that event is picked for further consideration on the duration.

Second, the symptom resolved date from both data sources (planned page and unscheduled page) will be slotted to different interval based on the relative day to each vaccination as illustrated below:

Third, if the event occurred on the last day of the e-Diary entry after dose 1 has a resolved date in the first period (after dose 1 but prior to dose 2), the ending date for that event will be used to calculate the symptom duration. If the event occurred after the specific dose with a symptom resolved date not in the same period (ie, e-diary is after dose 1 but symptom resolved date is after dose 2 or after dose 3), the duration for that event will be assigned as ‘Unknown’. At the same time, a query is sent to the site for confirmation if the duration indeed lasted more than one period.

If the site confirmed that the event did span to more than one period, the duration will be calculated as segment. For example, if the first day of the e-diary is day 2 of dose 1 and the ending date is day 40 after dose 3, and each day of the e-diary entry is presented with the symptom on dose 2 and dose 3, the duration for that subject at each dose period will be calculated as:

After dose 1: (Dose 2 date -1) – (Dose 1 date) +1

After dose 2: (Dose 3 date -1) – (Dose 2 date) +1

After dose 3: (Symptom resolved date) – (Dose 3 date) +1

In addition, the subjects with duration spanned to multiple dosing period will be footnoted with overall duration longitudinally.

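### For a reaction that runs past the next dose, the SAP's worked formula counts the dose 1 segment from the vaccination date instead of the onset day, one day too many in its own example

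*SAP*

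**What the plan says.** SAP 6.2.2.1 sets the general rule for local reactions: "the maximum duration (last day of reaction –first day of reaction +1) will be derived for each vaccination". SAP 6.2.2.2 derives the systemic-event variables in a similar way. SAP 6.2.2 fixes the day count: "The day of vaccination is considered as day 1".

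SAP 10.1.4.2.2 adds a special case. When a resolved date falls in a later dose period than the diary entry, the duration is first set to unknown and the site is queried. Then: "If the site confirmed that the event did span to more than one period, the duration will be calculated as segment". The illustration supposes "if the first day of the e-diary is day 2 of dose 1 and the ending date is day 40 after dose 3", and that "each day of the e-diary entry is presented with the symptom on dose 2 and dose 3". Its first segment is "After dose 1: (Dose 2 date -1) – (Dose 1 date) +1". The other two segments start at the dose 2 and dose 3 dates. Affected subjects also get a footnote with the overall duration, whose start day is not defined.

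**The concern.** The example states a start on day 2, but the onset day does not appear in the formula that follows. Subtracting the dose 1 date starts the count on day 1, when the example has no recorded reaction. The same segment therefore has two values, one under the general definition and one under the appendix, and a programmer cannot satisfy both.

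What is at stake is modest. SAP 8.2.5.1 summarises maximum duration by group after each vaccination, so an affected child would enter that table with a slightly inflated value. If the overall duration in the footnote were built by adding the segments, it would carry the same excess.

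**Working it through.** The plan states no numerical duration, so there is no figure to reproduce. The check is date arithmetic.

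**Inputs**
- Vaccination day is day 1 (SAP 6.2.2). Write D1, D2 and D3 for the dose dates; onset on day k is then the date D1 + (k − 1).
- The diary covers days 1 to 7 (SAP 6.2.2), so the latest recorded onset is k = 7.
- Dose 2 is 42 to 70 days after dose 1 (Protocol 6.1.4), so D2 − D1 = 42 to 70.
- Dose 3 is 105 to 126 days after dose 2 (Protocol 6.1.6), so D3 − D2 = 105 to 126.
- The example has k = 2, the symptom on every diary day after doses 2 and 3, and resolution on day 40 after dose 3.

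**Dose 1 segment, appendix formula**

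(D2 − 1) − D1 + 1 = D2 − D1, which gives 42 to 70 days.

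**Dose 1 segment, SAP 6.2.2.1 definition**

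(D2 − 1) − (D1 + k − 1) + 1 = D2 − D1 − (k − 1). With k = 2 this gives 41 to 69 days.

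**Excess**

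The difference is k − 1 days, whatever the interval between doses.

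| Onset day | Appendix formula | Definition | Excess |
|---|---|---|---|
| 1 | 42 to 70 | 42 to 70 | 0 |
| 2 (the SAP's example) | 42 to 70 | 41 to 69 | 1 day (2.4% to 1.4%) |
| 3 | 42 to 70 | 40 to 68 | 2 days (5.0% to 2.9%) |
| 7 | 42 to 70 | 36 to 64 | 6 days (16.7% to 9.4%) |

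**Later segments**

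The symptom is present from the first diary day after doses 2 and 3, so starting at the dose date is right.
- Dose 2 segment: (D3 − 1) − D2 + 1 = D3 − D2 = 105 to 126 days.
- Dose 3 segment: 40 days, reading day 40 as D3 + 39.

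**Overall duration**
- Sum of segments: 42 + 105 + 40 = 187, up to 70 + 126 + 40 = 236 days.
- Onset to resolution: onset is D1 + 1. Resolution is D1 + 42 + 105 + 39 = D1 + 186 at the short intervals and D1 + 70 + 126 + 39 = D1 + 235 at the long ones. That gives 186 to 235 days.
- The difference is again 1 day.

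**The case against.** The formulas are offered as an illustration of one case, reached only after a query and site confirmation. The SAP does not say that the dose 1 date is to be used for every onset day, so the 6-day figure extends the illustration to a case it does not cover. That stands, and 6 days is an upper bound only.

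The example's wording is loose. Its first e-diary day could mean the first transmitted entry and not onset, since SAP 6.3.1 says an incomplete day is not transmitted. This does not rescue the formula: day 1 would still be a day without a recorded reaction, and the general definition counts only from the first day of reaction.

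A reader might infer that the longest reported durations are wrong. They are not in this example. The longest segment follows dose 2 and is correct.

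A reader might also infer that the duration rules overstate duration in general, because the span "last day of reaction –first day of reaction +1" includes symptom-free days. A child affected only on days 1 and 7 would indeed score 7 days with 2 affected. The documents do not support calling this an error:
- The span is an openly stated convention. Nothing in either document sets a count of symptomatic days or an unbroken run as the standard.
- An unbroken reaction within one dose period is not overstated.
- The plan gives no background rate for isolated-day symptoms, so any size for the effect would rest on assumption.
- SAP 8.2.5.1 already summarises presence on each day and onset day, which shows intermittency at group level.
- A longest-run rule has its own cost. A reaction on days 1 to 3 and 5 to 7 with day 4 untransmitted would score 3 instead of 7.

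**Conclusion.** The dose 1 line of SAP 10.1.4.2.2 is wrong as written: it disagrees with the start day in its own example and with SAP 6.2.2.1. The excess is onset day minus 1, which is 1 day in the example and at most 6 days if the line were reused for a day 7 onset.

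The effect is confined to the segment in which a site-confirmed cross-dose reaction began. Such events should be rare, though the documents give no count. Duration is not among the primary safety endpoints (Protocol 2.2.2, SAP 6.2.1) or the endpoints that get between-group differences and p-values (SAP 8.2.5.1), and immunogenicity is untouched. This is a minor correction.

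The result rests on reading day 2 as the first day with the reaction and on the day-1 numbering in SAP 6.2.2. It needs no outside figure.

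**What to change.** In SAP 10.1.4.2.2, replace the dose 1 line with (Dose 2 date − 1) − (first day of reaction) + 1, and add that this start applies to the segment for whichever dose the reaction began after. State that the overall duration in the footnote also runs from the first day of reaction. Leave later segments starting at the dose date when the symptom is continuous; moving them back to the original onset would count earlier periods twice. Rewording the example so that day 2 is explicitly the onset day would remove the remaining ambiguity.

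The cost is a line or two of SAP text and a small programming change. The span definition in SAP 6.2.2.1 stays as it is.

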10.1.5. Additional Data Handling

10.1.5.1. Nonstudy Vaccine Date

This will impact the summary table of ‘Nonstudy Vaccine’. For all MnB studies, all previous use of PRP-OMP, and last dose of MCV4, Tdap, or HPV prior to study start will be entered in the nonstudy vaccine page labeled as ‘Prior xxx Use’. The concomitant vaccine administered after study start is required to be entered in the CRF page labeled as ‘Concomitant Vaccine’ (or label with similar meaning). All of the study only required the concomitant vaccine to be recorded after informed consent is signed till the one month after last study vaccine administration (or end of vaccination visit for early withdrawals).

- If the CRF page label indicates the nonstudy vaccine is collected in the designated ‘Prior xx Use’ page, this nonstudy vaccine will be summarized in the analysis interval of ‘prior to vaccination’ when the nonstudy vaccine administration is missing.
- If the CRF page label indicates the nonstudy vaccine is collected in the designated ‘Concomitant Vaccine Use’ page, this nonstudy vaccine will be summarized in the analysis interval of ‘Concomitant Vaccine’ when the nonstudy vaccine administration is missing.
- If a nonstudy vaccine is entered in the ‘Concomitant Vaccine Use’ page but the date indicates the nonstudy vaccine is administered prior to first dose of study vaccination, this nonstudy vaccine will not be summarized in the analysis interval of ‘Concomitant Vaccine’. Since ‘Prior xx Use’ page only collect certain prespecified vaccines, it will not be included in the summary of analysis interval of ‘prior to vaccination’. This nonstudy vaccine will be included in the nonstudy vaccine listing.
- If a nonstudy vaccine is entered in the ‘Concomitant Vaccine Use’ page but the date indicated the nonstudy vaccine is administered after the end of vaccination phase, this nonstudy vaccine will not be summarized in the analysis interval of ‘Concomitant Vaccine’. This nonstudy vaccine will be included in the nonstudy vaccine listing.

10.1.5.2. Nonstudy Medication Date

Pfizer general rule of imputing missing date of nonstudy medication may be used. However, summary table to include nonstudy meds used during the vaccination will not be provided, while a table to summarize all nonstudy medication use will be provided. Additionally, all original date (or partial date) in the database will be displayed in the listing. Therefore, the Pfizer imputation rule will not have any impact of the tables or listings.

10.1.5.3. All Subjects

Our safety population should include any vaccinated subjects, the ‘All Subjects’ should include subjects who were randomized or vaccinated; any subjects who were screen failure but not randomized will not be included as ‘All Subjects’.

10.1.5.4. Missing AE CRF / Incomplete AE CRF Information

Proportion of subjects with missing AE CRF will be calculated.

SAP [Section 7.2.2](#) describes the denominators and numerators. However, the main SAP section did not differentiate the ‘missing AE CRF for the **whole period**’ with ‘missing AE CRF for **some time** within analysis interval’. The latter is referred as ‘any incomplete AE CRF information’. Below paragraph describes the detailed data handling on calculating the numerators on ‘incomplete AE CRF information’.

This variable will be based on the ‘follow-up CRF’ page – as long as subject checked ‘yes’ on ‘Was AE discussed’ for a visit, this subject is not considered as with incomplete AE CRF information for any analysis interval prior to that visit or inclusive of this visit.

Table 12. Algorithm of Incomplete AE Safety Data Information

#	Analysis Interval	Analysis Population	Denominator	Numerator
1	Within 30 days after vaccination 1	Vaccination 1 Safety Population	# of subjects received vax 1	# of subjects with 'follow-up CRF' page checked as 'No' for all visits after vaccination 1
2	Within 30 days after vaccination 2	Vaccination 2 Safety Population	# of subjects received vax 2	# of subjects with 'follow-up CRF' page checked as 'No' for all visits after vaccination 2
3	Within 30 days after vaccination 3	Vaccination 3 Safety Population	# of subjects received vax 3	# of subjects with 'follow-up CRF' page checked as 'No' for all visits after vaccination 3
4	Within 30 days after any vaccination	Safety Population	# of subjects received any vax	# of subjects with 'follow-up CRF' page checked as 'No' for all visits after vaccination 1
5	During the vaccination phase	Safety Population	# of subjects received any vax	Same as above
6	During the follow-up Phase for Stage 1	Follow-up Safety Population for stage 1	# of subjects received any vax	# of subjects with 'follow-up CRF' page checked as 'No' for all visits after Visit 7 and up until Visit 8
7	During AE collection period	Safety Population	# of subjects received any vax	Total # of unique subjects from row #5 and row #6

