The Schedule of Activities provides an overview of the protocol visits and procedures. Refer to the Study Procedures and Assessments sections of the protocol for detailed information on each procedure and assessment required for compliance with the protocol.

The investigator may schedule visits (unplanned visits) in addition to those listed on the Schedule of Activities, in order to conduct evaluations or assessments required to protect the well-being of the subject.

Schedule of A	ctivities for	r Stage 1								
Visit Identifier	1	2	3	4 ^a	5	6	7	8	9	10
Time Period	Month 0	Week 1	Month 1	Month 2	Month 3	Month 6	Month 7	Month 12	Month 18	End of Stage 1
Visit Description	Vaccination 1	Post– Vaccination 1 Follow-up Visit	Telephone Contact	Vaccination 2	Post– Vaccination 2 Blood Draw	Vaccination 3	Post– Vaccination 3 Blood Draw	6-Month Follow- up Visit ^b	Antibody Persistence Blood Draw ^b	Telephone Contact
			Va	accination Pha	ise			Follow-up Phase		
Visit Window	Day 1 (Baseline)	7 to 10 Days After Visit 1	25 to 35 Days After Visit 1	42 to 70 Days After Visit 1	28 to 42 Days After Visit 4	105 to 126 Days After Visit 4	28 to 42 Days After Visit 6	168 to 196 Days After Visit 6	337 to 365 Days After Visit 6	-
Informed consent ^c	X									
Review eligibility criteria	X									
Confirm continued eligibility		X	Х	X	X	X	X	X	X	
Demography ^d	X									
Medical history ^e	X									
Physical examination ^f	X									
Vaccination History	X									

Visit Identifier	1	2	3	4 ^a	5	6	7	8	9	10
Time Period	Month 0	Week 1	Month 1	Month 2	Month 3	Month 6	Month 7	Month 12	Month 18	End of Stage 1
Visit Description	Vaccination 1	Post– Vaccination 1 Follow-up Visit	Telephone Contact	Vaccination 2	Post– Vaccination 2 Blood Draw	Vaccination 3	Post– Vaccination 3 Blood Draw	6-Month Follow- up Visit ^b	Antibody Persistence Blood Draw ^b	Telephone Contact
			V	accination Pha	ise			Follow-up Phase		
Visit Window	Day 1 (Baseline)	7 to 10 Days After Visit 1	25 to 35 Days After Visit 1	42 to 70 Days After Visit 1	28 to 42 Days After Visit 4	105 to 126 Days After Visit 4	28 to 42 Days After Visit 6	168 to 196 Days After Visit 6	337 to 365 Days After Visit 6	-
Brief physical examination ^g				X		X				
Heart rate, respiratory rate	X			X		X				
Axillary temperature	X			X		X				
Obtain 5-mL blood sample	X ^h				X		X	X	X	
Randomization	X									
Vaccination & 30-minute observation ⁱ	X			X		X				
Record nonstudy vaccinations		X	X	X	X	X	X	X	X	X

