7.2.2. Safety Data Collected Through CRF

Subjects are excluded from the analysis if they do not receive the vaccine dose or if safety data are missing for a specified interval.

The sponsor is making every effort to follow up with subjects for safety data (6-month after the last vaccination).

The missing data rate on the safety data in each analysis interval will be summarized for each group. The numerator will be the # of subjects with missing CRF safety data information. The denominators vary with the analysis interval.

#	Analysis Interval	Denominator
1	Within 30 days of vaccination 1	# of subjects received vax 1
2	Within 30 days of vaccination 2	# of subjects received vax 2
3	Within 30 days of vaccination 3	# of subjects received vax 3
4	Within 30 days of any vaccination	# of subjects received any vax
5	During the vaccination phase	# of subjects received any vax
6	During the follow-up Phase for Stage 1	# of subjects received any vax
7	During AE collection period (Visit 1 to Visit 8).	# of subjects received any vax

Further details about the data handling approach are available in the [appendix](#).

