10.1.5.4.1. Analyses Impacted

There are 5 safety populations defined: Safety Population; Vaccination 1 Safety Population; Vaccination 2 Safety Population; Vaccination 3 Safety Population, and Follow-up Safety Population for Stage 1. The analysis on the CRF related safety summary will use the corresponding safety population listed in [Table 12](#) as the population definition is the same as the denominator minus the numerator, except for the analysis interval of ‘During the AE collection period’.

The primary analysis on SAE, medically attended AE, newly diagnosed medical condition ‘During the AE collection period’ will use the overall ‘safety population’ because this will capture any events that were reported during the study stay regardless study/vaccination phase completion status.

Additional analysis will be performed on the follow-up safety population for stage 1 for the endpoints of SAE, medically attended AE, newly diagnosed medical condition during the AE collection period, so that the estimation are based on subjects with complete safety information.

Supplementary analyses may be performed on ‘SAEs during the AE collection period’ among subjects who completed the study; ‘(S)AE during the vaccination phase’ among subjects who completed the vaccination phase.

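### SAP Table 12 is presented as counting partly missing AE follow-up, but rows 1 to 5 count only children with no AE discussion at all, so the by-group incomplete rate is understated

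*SAP*

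**What the plan says.** SAP 7.2.2: "The missing data rate on the safety data in each analysis interval will be summarized for each group". Its numerator is children with missing CRF safety data, with no split by how much of the interval is missing.

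SAP 10.1.5.4 supplies that split. It separates AE CRF data missing for the entire interval from "missing AE CRF for some time within analysis interval", labels the second as incomplete information, and continues: "Below paragraph describes the detailed data handling on calculating the numerators on" that second category. Two statements of the rule follow.

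- **Prose.** Once AEs have been discussed on one occasion, "this subject is not considered as with incomplete AE CRF information for any analysis interval prior to that visit or inclusive of this visit".
- **Numerators in Table 12.** Row 4 (30 days after any vaccination) counts children with the follow-up CRF "page checked as 'No' for all visits after vaccination 1". Row 5 (vaccination phase) refers back to row 4. Rows 1, 2 and 3 use the same construction after vaccinations 1, 2 and 3. Row 6 (follow-up phase) requires a no at all visits after Visit 7 up to Visit 8. Row 7 is the union of rows 5 and 6.

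SAP 10.1.5.4.1 ties the safety populations to these counts: apart from the whole AE collection period, "the population definition is the same as the denominator minus the numerator".

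**The concern.** The section exists to distinguish partial from total absence of AE information and says it will count the partial kind. The table then counts the total kind. One early yes is enough to remove a child from the numerator of every interval that starts at Vaccination 1, however long that interval runs.

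What is at stake is the usefulness of a supporting table. The percentages with an AE, SAE, MAE or NDCMC over these intervals are primary safety endpoints (Protocol 2.2.2, SAP 6.2.1). The by-group incomplete rate is meant to tell the reader how completely each group was observed behind those percentages. If it omits children followed for only part of an interval, the data look more complete than they are.

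**Working it through.** The plan states no figure for this rate, so the check is of the counting rule.

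**Inputs** (Protocol Schedule of Activities, Stage 1; SAP Table 8)
- Visit 2: 7 to 10 days after Visit 1. Visit 3: "25 to 35 Days After Visit 1".
- Visit 4: 42 to 70 days after Visit 1. Visit 6: 105 to 126 days after Visit 4. Visit 7: 28 to 42 days after Visit 6.
- Vaccination phase: Visit 1 to Visit 7, or the end-of-vaccination date.
- Enrolment: about 396 (Protocol 9.1).

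**Step 1. Planned length of the vaccination phase.** Shortest: 42 + 105 + 28 = 175 days. Longest: 70 + 126 + 42 = 238 days. This ignores the possible extension of the Visit 4 window for sentinel children.

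**Step 2. A child with a yes at Visit 2 and no later contact.**
- Vaccination phase unobserved, least: 175 − 10 = 165 days, and 165/175 = 94%. Most: 238 − 7 = 231 days, and 231/238 = 97%.
- 30 days after Vaccination 1 unobserved: 30 − 10 = 20 to 30 − 7 = 23 days.
- Table 12 requires a no at all visits. This child has one yes, so is outside the numerators of rows 1, 4 and 5.

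**Step 3. Row 5 against the stated target.** Take the six contacts from Visit 2 to Visit 7 and let a yes cover all time back from that contact. Full cover then needs a yes at Visit 7.

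| Last yes | Row 5 as written | Missing for part of the interval |
|---|---|---|
| None | counted | counted |
| Visit 2, 3, 4, 5 or 6 (five patterns) | not counted | counted |
| Visit 7 | not counted | not counted |

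Of these seven dropout patterns, row 5 counts 1; the stated target would count 6. Over all 2^6 = 64 yes/no patterns, row 5 counts 1 and the target 32 (those with a no at Visit 7).

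**Step 4. The two readings of the prose.**
- If it clears every interval that contains the visit, a yes at Visit 2 clears the vaccination phase and the prose repeats row 5.
- If it clears only intervals that end at or before the visit, a yes at Visit 2 does not clear the vaccination phase and the prose contradicts row 5.

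Neither reading makes prose, table and stated purpose agree.

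**Step 5. Row 6 and absent pages.** Row 6 needs a page marked no. The SAP does not say what happens when there is no Visit 8 page. The Follow-up Safety Population (SAP 5.3) requires safety information after Visit 7 up to Visit 8, and the row 6 denominator is everyone vaccinated. For denominator minus numerator to give that population, a child with no such information must be in the numerator. The identity therefore requires an absent page to count as a no.

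**Step 6. Illustrative size.** Assume a fraction of the 396 children is lost after a yes at Visit 2: 2% gives 7.9, about 8; 5% gives 19.8, about 20; 10% gives 39.6, about 40; 20% gives 79.2, about 79. Row 5 counts none of them.

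**The case against.** The strongest reply is that this is a labelling fault in a supporting table and that the plan shows loss of follow-up elsewhere. Much of that stands.

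- **A reader might infer that the reported rate will be about zero in every row whatever the dropout.** The documents do not support this. By step 5, children with no information after Visit 7 belong in row 6, and row 7 takes them from there. The understatement is shown for rows 1 to 5. Even there, children with a no at every visit are counted.
- **A reader might infer that dropout differing between arms would be hidden.** It would not be. SAP 8.2.6.1 tabulates withdrawals and completion by phase and randomized group, with reasons. SAP 8.2.7 separates full-series from partial-series children. SAP 10.1.5.4.1 adds an analysis on the follow-up population and allows completer analyses. SAP 8.2.5.2.7 scales event counts by days on study. None of these gives AE coverage by interval, which is what Table 12 is for.
- **A reader might infer that the AE percentages are wrong.** Keeping partly observed children in the Safety Population is intended and stated in 10.1.5.4.1.
- **Early withdrawals.** SAP Tables 8 and 11 end the vaccination phase early for them, so a formally withdrawn child could be called complete for a shortened interval. Table 12 does not say that this applies, and its denominator is everyone vaccinated.
- **Telephone contact.** Protocol 6.1.12 plans an AE call about 6 months after the last vaccination for children who withdraw before Visit 8. It will recover some information, but not from families who cannot be reached.
- **Visit 3.** A call on day 25 to 29 leaves the 30-day interval slightly short, but a later yes closes the gap. This is minor.
- **The 20% figure.** In Protocol 9.1 it is an allowance for children nonevaluable for immunogenicity. It is not a rate of lost AE contact and serves here only as a generous upper end.

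**Conclusion.** The point holds for Table 12 rows 1 to 5. They implement missingness of the whole interval under a label and a stated purpose that promise partial missingness, so the by-group incomplete rate in SAP 7.2.2 is understated. The clearest case is a child last asked about AEs at Visit 2, who is not counted as incomplete in rows 1, 4 or 5 with about 94% to 97% of the planned vaccination phase unobserved. The conclusion rests on the table more than on the prose rule, which is ambiguous. Row 6 has a smaller gap: the treatment of an absent page is unstated, although the population identity settles what it must be.

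The number of children affected depends on dropout, which the documents do not give. The illustration of 8 to 79 of 396 assumes that 2% to 20% are lost after a yes at Visit 2 and are not reached later. The effect is confined to the reported completeness of AE follow-up.

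**What to change.** Report two numerators for each interval in Table 12.

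- **(a) No AE information at all.** This is the present count. State in 10.1.5.4.1 that it alone continues to define the safety populations, so that partly observed children are not removed from them.
- **(b) Incomplete.** No yes to AE discussion at a contact on or after the interval's stop date. For rows 1 to 3, that means at least 30 days after that vaccination; for row 4, the same for each dose received; for row 5, Visit 7 or later; for rows 6 and 7, Visit 8 or the 6-month telephone contact.

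Also state that an absent page counts as a no, state whether the shortened interval for early withdrawals in Tables 8 and 11 applies to (b), and reword the prose rule to match. One detail needs a decision: Visit 7 may fall on day 28 or 29 after Vaccination 3, just short of the 30-day stop date. The SAP should say whether an in-window Visit 7 satisfies row 3 and the Vaccination 3 part of row 4.

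The cost is SAP wording and programming from visit dates already collected. The downside is that the reported incomplete rates become less favourable.
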